2. BACKGROUND AND RATIONALE

2.1 Diffuse Midline Gliomas

Diffuse midline gliomas (DMGs), formerly known as diffuse intrinsic pontine gliomas (DIPG) and thalamic gliomas, constitute 10% of all pediatric central nervous system (CNS) tumors. DMG is a WHO grade IV glioma that arises in the pons, thalamus and other midline structures. The most common type is a diffusely infiltrating astrocytoma (diffuse intrinsic pontine glioma – DIPG). Subjects with DIPG have a poor prognosis - median survival is usually reported to be 9 months, and nearly 90% of children die within 18 months from diagnosis [1-11]. In the molecular era, biopsies for DIPG are considered standard of care (SOC) for diagnostic purposes. The mainstay of treatment is radiation, typically to a dose of 54 Gy to the primary tumor site. No benefit from doses up to 78 Gy has been seen [8]. Surgical resection does not influence outcome [12] and is often not feasible in this extremely eloquent part of the central nervous system. Numerous

studies of systemic chemotherapy have all failed to demonstrate any significant improvement in survival, despite at times using very intensive chemotherapy regimens. This repeated failure of systemic therapy is, in part, due to an intact blood brain barrier (BBB), which limits drug access to the tumor.

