10.1 Sample Size Determination

A minimum of 3 and maximum of 15 patients will be recruited in the study. The minimum number of subjects is to account for “dose” limiting toxicities disallowing more subjects to be enrolled. As this is a feasibility study, the power and sample size is not justified. However, successful methodology will be concluded if the BBB opening is safely opened in at least 75% of the cases as evidenced on MRI. The scan with the BBB opening will be compared to the scan before BBB opening for each patient. Power analysis shows that for a detectable difference of 72 mm^3 (after BBB opening - before BBB opening) and a standard deviation of 50 mm^3 , at least 6 subjects are needed to report a result at the level of $\alpha=0.05$ and Power=0.80 with paired student's t-test.

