12.2 Dose Limiting Toxicities

Dose limiting toxicities (DLT) will be defined as any new (or increased from baseline), treatment related (drug and/or device):

1. Neurological deficits based on neurological examination which are grade 3 or greater nervous system adverse events at least possibly attributed to sonication (as defined by CTCAE v5.0).

2. Grade 2 or higher symptomatic intracranial hemorrhage or stroke.

These deficits include but are not limited to changes in level of consciousness, new onset speech difficulties (aphasia, mutism, dysarthria), confusion, visual field deficits, focal weakness, seizures. The DLT period is defined as starting the day of the first scheduled FUS treatment and lasting until 14 days after the last scheduled FUS treatment.

Furthermore, DLT criteria include any systemic treatment- related Grade 3 or higher hematologic or non-hematologic toxicity within a period of 14 days after the scheduled FUS treatment. Examples of exceptions could include:

- I. Grade 3 thrombocytopenia without bleeding, Grade 3 or 4 lymphopenia, Grade 3 neutropenia without fever.
- II. Nausea, vomiting or diarrhea responding to medical management within 48 hours
- III. Electrolyte disturbances that are asymptomatic and response to supportive care within 48 hours; hyperglycemia \leq 12 hours

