12.3 Early Stopping Guidelines

In the event 2 DLTs occur for more than 1 subject at a NOTS (number of tumor sites) level (as defined in [section 7.2](#)), study enrollment will be immediately halted. There will be at least 14 days following completion of the FUS treatment of the patient(s) on study before any subsequent patient is enrolled. After re-evaluation and consultation with the HICCC DSMC board, the trial may re-initiate enrollment with adjusted treatment parameters after a consensus is agreed upon by the Sponsor-Investigator and the HICCC DSMC, and a subsequent modification is reviewed/approved by the local PRMC/IRB. If a consensus cannot be reached, no further enrollment will be permitted on the trial and closure procedures will be initiated. In addition, the study will be discontinued at any given time if more than 20% of patients experiencing medical complications including the development of significant, irreversible deterioration during the treatment. With this rule and under the assumption of the true probability of having the medical complication is 10%, the probability of stopping the study due to the medical complication is 0.02 when the targeted total sample size is 6 and is 0.053 when the targeted total sample size is 9.

If the MRI to confirm opening of the BBB for any subject is irregular at any time during the cycles, the subject will not receive the scheduled dose treatment until a decision is made by the investigating team.

If the MRI confirm the closure of the BBB for any subject are irregular at any time, the subject will not receive any further FUS treatments and will receive another MRI to confirm closure every 48 hours for a maximum of 3 times. If the subject does not show BBB closure after 3 MRIs, the subject will come off the study. The subject will be able to receive the scheduled dose of drug, unless otherwise specified by the investigating team.

Response and progression will be evaluated in this study using the international criteria proposed by the updated Pediatric Response Assessment in Neuro-oncology (RANO) guidelines[49].

| Criterion | Complete Response | Partial Response | Stable Disease | Progressive Disease |
|----------------------------------------|---------------------|---------------------|---------------------------------|---------------------|
| T1-weighted post-Gd measurable disease | None | ≥50% decrease | <50% decrease but <25% increase | ≥25% increase |

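### The 20% complication stopping rule in 12.3 does not say whether disease deterioration counts, and its stated stopping probabilities do not describe the rule as written

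*Combined protocol and SAP*

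**What the plan says.** Section 12.3 contains two study-level rules: one on dose-limiting toxicities at a given number of tumour sites, and a second on complications. The second has no timetable of looks: "the study will be discontinued at any given time". Its trigger reads: "if more than 20% of patients experiencing medical complications including the development of significant, irreversible deterioration during the treatment". The term for the counted event is not defined elsewhere, and the sentence does not say whether the event must be related to treatment.

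The rule's operating characteristics are worked out "under the assumption of the true probability of having the medical complication is 10"%, a rate given without a source. The result reported for the smaller case is this: "the probability of stopping the study due to the medical complication is 0.02 when the targeted total sample size is 6". For the larger case, the figure "is 0.053 when the targeted total sample size is 9". Section 10.1 allows more patients than either case: "A minimum of 3 and maximum of 15 patients will be recruited in the study".

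Two neighbouring rules do attribute. Section 12.2 defines a dose-limiting toxicity as "any new (or increased from baseline), treatment related (drug and/or device"). Section 12.6 terminates the investigation for deaths and serious events caused by the procedure.

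On the disease, section 2.1 says of the pontine form that "median survival is usually reported to be 9 months, and nearly 90% of children die within 18 months from diagnosis". Section 8.1.1 enrols only patients whose tumour has already progressed.

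**The concern.** Every patient enters with progressive diffuse midline glioma, so serious and lasting deterioration during treatment is a foreseeable result of the disease. If the 12.3 rule counts it, the relevant rate is disease background plus treatment harm, and 10% looks too low. If the rule does not count it, an attribution step is being applied that the sentence does not contain.

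Both cases matter because safety is the primary endpoint. Counting everything, the study could be discontinued for natural history with the safety question unanswered. Filtering by an unwritten judgement, the rule depends on case-by-case decisions and its stated stopping probabilities cannot be verified. A reader relying on 0.02 and 0.053 would believe that false stopping is rare.

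**Working it through.** **Step 1: the plan's own figures.** Inputs from 12.3: threshold above 20%, true rate 0.10, 6 or 9 patients. The formula is the binomial tail P(X ≥ r) for n patients at rate p. More than 20% means at least 2 of 6 (33%), 2 of 9 (22%) and 4 of 15 (27%).

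| n | r | P(X ≥ r) at 0.10 | Stated |
|---|---|---|---|
| 6 | 2 | 0.114 | 0.02 |
| 6 | 3 | 0.016 | 0.02 |
| 9 | 2 | 0.225 | 0.053 |
| 9 | 3 | 0.053 | 0.053 |
| 15 | 4 | 0.056 | none |

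For example, n = 6, r = 2: 1 − 0.9^6 − 6(0.1)(0.9^5) = 1 − 0.531 − 0.354 = 0.114. Of the boundaries tried (1 to 4 events, and repeated looks), only at least 3 events gives both stated values. That is 50% of 6 and 33% of 9, which is not the written threshold.

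The table assumes a single final look. Looking after every third patient, the written rule at 0.10 stops with probability 0.29 (n = 6), 0.35 (n = 9) and 0.36 (n = 15), partly because one event among the first three already exceeds 20%.

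**Step 2: an assumed disease background.** The documents give no rate of irreversible deterioration in progressed patients. The only survival figures for this disease are those in 2.1, for death counted from diagnosis. Exposure comes from 7.5: six two-week cycles with one-week gaps. Cycle 6 starts on day 1 + 5 × 21 = 106, and its last ultrasound falls on day 5 of its second week, day 117. That is 117/30.44 = 3.84 months.

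- Exponential through a 9-month median: 1 − 2^(−3.84/9) = 0.256.
- Exponential through 90% dead at 18 months (implied median 18·ln 2/ln 10 = 5.42 months): 1 − 2^(−3.84/5.42) = 0.388.
- Weibull through both points: shape k = ln(ln 10/ln 2)/ln 2 = 1.732, scale 9/(ln 2)^(1/k) = 11.12 months; 1 − exp(−(3.84/11.12)^1.732) = 0.147, about 0.15, with the clock started at diagnosis.
- The same Weibull, conditional on entry 3, 6 or 9 months after diagnosis (entry times assumed): 0.28, 0.37, 0.45.

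**Step 3: stopping probability with no treatment harm, single look.**

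| Assumed rate | ≥2 of 6 | ≥2 of 9 | ≥4 of 15 | ≥3 of 6 | ≥3 of 9 |
|---|---|---|---|---|---|
| 0.15 | 0.22 | 0.40 | 0.18 | 0.05 | 0.14 |
| 0.256 | 0.48 | 0.71 | 0.56 | 0.18 | 0.42 |
| 0.388 | 0.75 | 0.92 | 0.89 | 0.43 | 0.75 |

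The first three probability columns are the written rule. The last two are the boundary behind the stated figures. Looking after every third patient, the written rule gives 0.42/0.52/0.55, 0.66/0.79/0.82 and 0.85/0.94/0.97 (n = 6/9/15) at the three rates.

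The rate at which stopping reaches 50% at one look is 0.26 (2 of 6), 0.18 (2 of 9), 0.24 (4 of 15), 0.42 (3 of 6) and 0.29 (3 of 9).

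**The case against.** A reader might infer that the disease alone is known to exceed 10%, so that the rule would probably stop a safe trial. The documents do not support that as a finding.

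- **The background rate is extrapolated.** Section 2.1 reports death from diagnosis, not irreversible deterioration after progression. Neither exponential fits both of its figures: a 9-month median implies only 75% dead at 18 months. The curve that fits both gives the lowest rate, 0.15, and single-look stopping below one half at every sample size.
- **The counting window may be short.** Section 9.1 ends the treatment period at progression, and under the response table in 12.3 reduced clinical status alone is progression. Decline after that point may not be counted. Entry also requires a performance score of at least 70 (8.1.2).
- **An attributed reading is available.** The sentence follows a toxicity rule, and 10% is a natural figure for treatment complications. All-cause counting could also be a deliberate conservative choice where attribution is difficult.

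A second tempting step is to attribute the whole distance between 0.02 or 0.053 and the Step 3 figures to natural history. That mixes boundaries. Going from three events to two at 10% already moves 0.016 to 0.114 and 0.053 to 0.225.

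Much of this stands, and it limits the claim. It does not remove the problem. Later entry and deterioration short of death push the rate up. An event that itself marks progression may still count as occurring during treatment. And if attribution is intended, the sentence does not say so.

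**Conclusion.** The point holds in limited form. The 12.3 rule leaves its counted event undefined and unattributed, unlike 12.2 and 12.6, while its operating characteristics use an unsourced 10% that is hard to reconcile with all-cause deterioration in children who have already progressed. Read literally, the rule may stop a trial of a harmless treatment. How likely that is depends on an assumed background rate, and 0.15 to 0.39 is a range of extrapolations that could be too high or too low. Under the three-event boundary, stopping is the more likely outcome only for 9 patients towards the upper end of that range.

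The arithmetic finding needs no assumption about the disease. At the plan's own 10%, the written rule stops with probability 0.114 and 0.225 at one look, not 0.02 and 0.053. The stated figures also leave out repeated looks and sample sizes between 10 and 15.

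**What to change.** Reconcile 12.3 with 12.2 and 12.6 so that the counted event and the assumed rate are the same quantity. There are two coherent ways:

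- count complications attributed to study treatment, and report disease deterioration separately; or
- count events of any cause, and use an assumed rate that includes the disease background, with its source or a stated range.

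Under either, say whether an event that itself marks progression falls within treatment. Under the first, also say how the rule relates to 12.6, which already terminates for serious events due to the procedure. Then write the boundary as event counts at each number of patients, state when it is checked, and recompute the stopping probabilities for that boundary with its repeated looks, up to 15 patients.

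The cost is a short rewording and a recalculation. The attributed option needs a judgement for each event. Section 11.1 already requires attribution to study procedures, and this would have to cover the drug as well. The restated probabilities are likely to look less favourable than the present ones.

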12.4 Early Withdrawal of Subjects

- If the subject fails to comply with the defined treatment plan and follow-up evaluations, the subject may be removed from the study at the discretion of the treatment investigator
- If the subject withdraws consent for continued participation, he/she will be removed from the study
- If the subject develops significant, new neurologic deficits or a change in level of consciousness a CT or MR scan may be performed to evaluate for hemorrhage/edema. If symptoms remain unmanageable by medications, craniotomy may be performed for resection of tumor, necrosis, or hemorrhage if medically indicated
- The reason for study removal and the date the subject was removed should be documented in the Case Report Form (CRF)
- If the treatment related toxicity experienced toxicity (Grade 2 or higher) persists for more than 21 days or ≥1 Dose Limiting Toxicity, the subject will not have the subsequent FUS and early withdrawal will be considered.

The primary endpoint of this study is safety. As such, subjects will be withdrawn from the study as per the guidelines outlined above. Should similar toxicities occur in more than one subject; early interruption of the study will be considered.

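### The stopping probabilities in section 12.3 (0.02 for 6 subjects, 0.053 for 9) belong to a 3-event trigger, but the written 20% rule is met by 2 events, which gives 0.114 and 0.225

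*Combined protocol and SAP*

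**What the plan says.** The rule, in section 12.3 (Early Stopping Guidelines), is that "the study will be discontinued at any given time if more than 20% of patients experiencing medical complications", with significant irreversible deterioration during treatment given as an included case. The next sentence opens with a reference back to this rule, assumes a true complication probability of 10%, and gives two results: "the probability of stopping the study due to the medical complication is 0.02 when the targeted total sample size is 6 and is 0.053" for a targeted total of 9.

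The rule is expressed only as a percentage. No event count is given, and no other section sets the trigger at three complications. Section 12.3 does not say whether the percentage is of the targeted total or of the subjects treated so far, or from which subject it starts to apply.

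On size, section 10.1 says: "A minimum of 3 and maximum of 15 patients will be recruited in the study". No stopping probability is given for 15. Section 12.4 adds: "The primary endpoint of this study is safety".

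**The concern.** The threshold, the assumed rate and the two sample sizes are all printed, so the probabilities can be checked directly, and they look too small. With 6 or 9 subjects, a threshold just above 20% is crossed by the second event. Two or more events at a 10% rate are not rare enough to give 0.02 or 0.053.

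These are the only probabilities the protocol gives for any stopping rule, in a trial whose primary endpoint is safety. The data and safety monitoring committee and the IRB would read them as saying that, at a 10% complication rate, the rule stops a study of 6 or 9 subjects 2% to 5% of the time. The text and the figures also imply different actions. With two complications among 6 or 9 subjects, the wording discontinues the study, while the calculation assumes that it continues.

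**Working it through.** **Inputs, all from section 12.3 unless noted.** Threshold: strictly more than 20%. True complication probability: p = 0.10. Targeted totals: n = 6 and n = 9. Maximum n = 15 (section 10.1).

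**Step 1: reproduce the printed figures.** With X ~ Binomial(n, 0.10), take three or more events.

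- n = 6: P(X ≥ 3) = 1 − 0.9⁶ − 6(0.1)(0.9⁵) − 15(0.1²)(0.9⁴) = 1 − 0.5314 − 0.3543 − 0.0984 = 0.0159, which rounds to the printed 0.02.
- n = 9: P(X ≥ 3) = 1 − 0.9⁹ − 9(0.1)(0.9⁸) − 36(0.1²)(0.9⁷) = 1 − 0.3874 − 0.3874 − 0.1722 = 0.0530, the printed 0.053.

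Both printed values are therefore those of a 3-event trigger.

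**Step 2: find the count at which the written rule is met.**

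| n | 1 event | 2 events | Smallest count above 20% |
|---|---|---|---|
| 6 | 16.7% | 33.3% | 2 |
| 9 | 11.1% | 22.2% | 2 |

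**Step 3: compute the probability for that count.**

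- n = 6: P(X ≥ 2) = 1 − 0.5314 − 0.3543 = 0.1143. Ratio to the printed value: 0.1143/0.02 = 5.7 (7.2 against the unrounded 0.0159).
- n = 9: P(X ≥ 2) = 1 − 0.3874 − 0.3874 = 0.2252. Ratio: 0.2252/0.053 = 4.2.
- n = 15: 3/15 is exactly 20% and does not exceed it, so 4 events are needed. P(X ≥ 4) = 0.056.

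**Step 4: ask whether a mistyped percentage explains the gap.** With denominators of 6 and 9, a rule of more than t triggers at exactly 3 events if 2/6 ≤ t < 3/6 at n = 6, and if 2/9 ≤ t < 3/9 at n = 9. Because 2/6 = 3/9, the two ranges do not overlap. A rule of at least t fails in the same way: t must be above 33.3% at 6 and no more than 33.3% at 9. No single percentage of those two totals gives both printed figures.

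**Step 5: allow for a running percentage.** The rule applies at any time, so it may be meant as events divided by subjects treated so far. The protocol gives no schedule of looks; the three below are assumptions, used to show the range. Each entry is the exact probability that the observed proportion exceeds 20% at one or more looks, with p = 0.10.

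| Looks (assumed) | n = 6 | n = 9 | n = 15 |
|---|---|---|---|
| After every subject, no minimum | 0.350 | 0.397 | 0.418 |
| After each 3 subjects | 0.291 | 0.354 | 0.364 |
| After every subject from the 5th | 0.114 | 0.225 | 0.260 |

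Most of the 0.350 comes from a single event among the first four subjects, which already exceeds 20%: 1 − 0.9⁴ = 0.344. None of these schedules moves towards 0.02 or 0.053.

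**The case against.** The best attempt to rescue the figures takes the denominator to be the maximum of 15. Twenty per cent of 15 is exactly 3 events, so a rule of at least 20% of 15 would trigger at the third event whether 6 or 9 subjects had been treated, and would give 0.0159 and 0.0530. This shows that the conclusion in step 4 holds only for denominators of 6 and 9. It does not save the text, which requires the percentage to be exceeded and calls 6 and 9 the targeted totals.

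A second argument is that the error does little harm. The operative instruction is the percentage; the probabilities only describe it and trigger nothing. Staff following the wording at a total of 6 or 9 would act at two events, so the rule stops more readily than advertised. No sample size or analysis depends on the figures: section 10.1 disclaims a power justification and section 10.2 makes the analysis descriptive. Other safeguards would often act first, namely the limits tied to dose-limiting toxicity in sections 12.1 and 12.3, the provision on similar toxicities in section 12.4, the termination rule in section 12.6 and the discontinuation rule in section 13.3. All of this stands, and it means that subject protection does not rest on these two numbers. It does not make the numbers right, and the 20% rule is not limited to procedure-related events, so it is not redundant.

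Two limits of scope also stand. The contrast between 2% to 5% and 11% to 23% applies to totals of 6 and 9 only; at a fixed total of 15 the figure is 0.056. The running-percentage results rest on assumed looks and illustrate the ambiguity; the error is established without them.

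**Conclusion.** The concern holds. At a true rate of 10%, the rule as written stops the study with probability 0.114 for 6 subjects and 0.225 for 9, when judged once on the full total. The protocol prints 0.02 and 0.053, which match a trigger of three events that it states nowhere. Using more than 2 events in place of 2 or more would produce this pattern, but the documents do not confirm that cause.

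The result assumes independent complications with a common probability of 10%, which is the protocol's own assumption for the rate, and a denominator of 6 or 9, which is how the protocol frames its figures. If a running percentage is meant and includes a look at the full total, 0.114 and 0.225 are lower bounds. What is wrong is the account of the rule's behaviour given to the oversight bodies, together with the unresolved difference between a 2-event and a 3-event trigger.

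**What to change.** Reconcile the rule and its probabilities in section 12.3.

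- If the 20% wording stands, replace 0.02 and 0.053 with 0.114 and 0.225, or with sequential figures computed for a stated schedule if a running percentage is meant.
- If three events is the intended trigger, state it as an event count, since no single percentage of the totals gives it at both 6 and 9. The printed figures then hold (0.016 and 0.053 to three decimals).
- In either case, state whether the denominator is the targeted total or the subjects treated so far, and from which subject the rule applies.
- Add the figure for the maximum of 15. Under the 20% wording this is 0.056 for a fixed total, or 0.26 to 0.42 for a running percentage under the three schedules shown.

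Which threshold is right is for the sponsor to decide. The cost is protocol wording only, with no change to sample size, endpoint or analysis. If the 20% wording is kept, the stated stopping probabilities at 6 and 9 become less favourable.

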3.1.4 Risks Associated with Panobinostat

The most common adverse reactions (incidence of at least 20%) in clinical studies are diarrhea, fatigue, nausea, peripheral edema, decreased appetite, pyrexia, and vomiting.

The most common non-hematologic laboratory abnormalities (incidence $\geq 40\%$) are: Hypophosphatemia, hypokalemia, hyponatremia, and increased creatinine.

The most common hematologic laboratory abnormalities (incidence $\geq 60\%$) are: thrombocytopenia, lymphopenia, leukopenia, neutropenia, and anemia.

Panobinostat carries a boxed warning alerting patients and health care professionals that severe diarrhea and severe and fatal cardiac events, arrhythmias and electrocardiogram (ECG) changes have occurred in patients receiving Panobinostat.

Other notable adverse drug reactions of Panobinostat not described above, which were either clinically significant, or occurred with a frequency less than 10% but had a frequency in the Panobinostat arm greater than 2% over the control arm in the multiple myeloma clinical trial are listed below:

Infections and infestations: hepatitis B.

Endocrine disorders: hypothyroidism.

Metabolism and nutrition disorders: hyperglycemia, dehydration, fluid retention, hyperuricemia, hypomagnesemia.

Nervous system disorders: dizziness, headache, syncope, tremor, dysgeusia.

Cardiac disorders: palpitations.

Vascular disorders: hypotension, hypertension, orthostatic hypotension.

Respiratory, thoracic and mediastinal disorders: cough, dyspnea, respiratory failure, rales, wheezing.

Gastrointestinal disorders: abdominal pain, dyspepsia, gastritis, cheilitis, abdominal distension, dry mouth, flatulence, colitis, gastrointestinal pain.

Skin and subcutaneous disorders: skin lesions, rash, erythema.

Musculoskeletal and connective tissue disorders: joint swelling.

Renal and urinary disorders: renal failure, urinary incontinence.

General disorders and administration site conditions: chills.

Investigations: blood urea increased, glomerular filtration rate decreased, blood alkaline phosphatase increased.

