6.2 Secondary Objective

- To evaluate the 6-month Progression Free Survival (PFS6) and 6-month Overall Survival (OS6)
- To determine blood brain barrier/tumor imaging changes using FUS in children with progressive DMG

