9. FOLLOW-UP

9.1 Duration of Therapy and Follow-up

The treatment period of this study begins at the time of the NgFUS ultrasound and concludes upon evidence of progression . Patients will be monitored for AEs and SAEs for up to 90 days post completion of study. During follow-up the study team will be responsible for conducting a physical exam, repeating MRI (if indicated by the primary physician), and collecting survival data.

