| T2/FLAIR | Stable or decreased | Stable or decreased | Stable or decreased | Increased |
| New lesion | None | None | None | Present |
| Corticosteroids | None | Stable or decreased | Stable or decreased | NA |
| Clinical status | Stable or increased | Stable or increased | Stable or increased | Decreased |
| Requirement for response | All | All | All | Any |

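### As printed, the response table in section 12.3 makes any fall in clinical status progressive disease, so decline not caused by tumor would be scored as a PFS6 event

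*Combined protocol and SAP*

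**What the plan says.** Section 12.3 introduces the table with "Response and progression will be evaluated in this study using the international criteria proposed by the updated Pediatric Response Assessment in Neuro-oncology (RANO) guidelines[49"]. The two rows that matter are "Clinical status | Stable or increased | Stable or increased | Stable or increased | Decreased" and "Requirement for response | All | All | All | Any". The columns run complete response, partial response, stable disease, progressive disease. Stable disease therefore needs every criterion, including a clinical status that has not fallen, while progressive disease needs only one.

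Progression is used in two places. Section 6.2 lists PFS6 with OS6 as a secondary objective and does not define a PFS event. Section 9.1 says that the treatment period "concludes upon evidence of progression". Section 10.2 describes the analysis as descriptive and gives no event or censoring rule for PFS6.

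Two other sections describe declines that need not come from tumor. Section 3.1.4 states: "The most common adverse reactions (incidence of at least 20%) in clinical studies are diarrhea, fatigue, nausea, peripheral edema, decreased appetite, pyrexia, and vomiting". Section 12.2 lists as neurological DLT signs "changes in level of consciousness, new onset speech difficulties (aphasia, mutism, dysarthria), confusion, visual field deficits, focal weakness, seizures".

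**The concern.** A progression endpoint should record tumor progression. Here the clinical row is sufficient alone and does not ask why the subject is worse, by how much, on which scale, or for how long. The treatment has known systemic toxicity, and the procedure is being tested precisely because it may cause neurological deficits. Falls in clinical status without tumor growth are therefore foreseeable.

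What is at stake is the meaning of PFS6. If toxicity and intercurrent illness count as events, PFS6 becomes a mixture of tumor control and tolerability. With at most 15 subjects, one or two such events visibly change the reported figure.

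**Working it through.** The plan states no PFS6 rate, target or power, so there is no figure to reproduce. The check is mainly a reading of the rule, followed by arithmetic for scale.

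**1. Is a clinical decrease sufficient alone?** Yes. The progressive-disease column has *Decreased* for clinical status and *Any* as the requirement.

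**2. Does the table offer another category?** No. Stable disease needs *All* criteria, so a subject with unchanged imaging and a lower clinical status cannot be scored stable. There is no not-evaluable category.

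**3. Does any other text qualify the row?**
- Sections 6.2, 9.1, 10 and 10.2, and the text around the table, give no cause, size, scale or confirmation.
- Karnofsky/Lansky status is collected (section 8.1.2, Appendices A and B) but is not tied to clinical status in the table.
- The corticosteroid entry for progressive disease is NA, so a steroid change does not qualify a clinical decrease.
- Section 12.2 does attach treatment-relatedness and grade floors to DLTs. It does not say that a DLT is excluded from progression.

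**4. Three hypothetical records, scored literally, all with unchanged MRI:**
- Fatigue or diarrhea from panobinostat lowers clinical status, and the subject then recovers: progressive disease. Section 12.2 gives diarrhea that responds to management within 48 hours as an example of an exception to DLT, so an event too minor to be a DLT can still be progression.
- Grade 3 weakness possibly attributed to sonication: a DLT under 12.2 and also progressive disease under 12.3.
- An intercurrent infection with a worse status on the assessment day: progressive disease.

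**5. Weight of one event.** If the subject would otherwise be progression-free at 6 months, the change in PFS6 is 100/n points. Section 10.1 gives n from 3 to 15.
- n=15: 100/15 = 6.7
- n=9: 100/9 = 11.1
- n=6: 100/6 = 16.7
- n=3: 100/3 = 33.3

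**6. Illustration only.** Let S be the true PFS6 and q the probability of a non-tumor clinical decrease within 6 months, independent of progression. Scored PFS6 = S × (1 − q). Neither S nor q is in the documents. For assumed S from 0.20 to 0.50:
- q=0.10: 0.20 × 0.90 = 0.18 to 0.50 × 0.90 = 0.45
- q=0.20: 0.20 × 0.80 = 0.16 to 0.50 × 0.80 = 0.40
- q=0.30: 0.20 × 0.70 = 0.14 to 0.50 × 0.70 = 0.35

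At an assumed S of 0.40, the shift is 0.04 to 0.12. At n=15 that is 15 × 0.04 = 0.6 to 15 × 0.12 = 1.8 subjects. I give no calculation per visit: Appendix B marks performance status under Day 1 without saying that it is repeated each cycle, so the number of assessments would be a further assumption.

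**The case against.** The strongest reply is that the grid summarizes a cited guideline, and that the guideline may limit a clinical decrease by cause or size. That cannot be checked from the documents. It leaves room for investigators to apply such limits, but it does not put them in the plan. The text names a pediatric guideline, while the reference entry is titled for high-grade gliomas without mention of children, so a reader cannot tell which outside qualifiers would apply.

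It is also fair to say that no passage states outright that toxicity is a PFS6 event. The step from table to endpoint is an inference. It is a close one, because no other definition of progression exists.

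A reader might go further and infer that an event called progression disappears from the DLT count and so weakens the primary safety outcome. The documents do not support this. Nothing makes DLT and progression mutually exclusive. Section 12.2 needs only a possible attribution to sonication for a neurological DLT, and section 6.1 has adverse events recorded irrespective of causality.

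A reader might also infer a firm conflict between section 9.1, where progression ends treatment, and section 12.1, where treatment may resume as toxicity resolves. Section 9.1 does not cite the table, and a subject with a DLT already comes off study under sections 7.2 and 12.1. The clash arises only if recognized, recovering toxicity is scored by the letter of the table.

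**Conclusion.** The point stands for PFS6. The rule as printed scores a non-tumor or transient fall in clinical status as progression, and nothing in the documents corrects it. Against a PFS6 that counts tumor progression and death, the error runs one way: extra events can lower the estimate or leave it unchanged, never raise it. Each affected subject who would otherwise be progression-free costs 6.7 points at n=15 and 16.7 at n=6.

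The conclusion rests on two assumptions: that the table defines the PFS6 event, and that it is applied as printed without qualifiers from the cited guideline. The total bias cannot be estimated, because the rate of non-tumor decline is not given; the range in step 6 shows scale only. PFS6 is secondary and descriptive with no decision rule, so no power or error rate is affected. OS6 and the DLT count are not shown to be affected.

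**What to change.** Add a footnote to the 12.3 table covering these points for PFS6:
- A clinical-status decrease counts as progressive disease only if the investigator judges it attributable to tumor and not to study-treatment toxicity or intercurrent illness.
- It should be supported by imaging progression, or by persistence at a later assessment where one exists, and dated to the first decrease. If no later assessment exists, the attribution judgement stands. Confirmation should not be mandatory, because subjects with a DLT come off study and section 12.5 calls for at least survival data on withdrawn subjects.
- A DLT is still counted as a DLT whatever the progression call, and is not by itself a PFS6 event.
- State how subjects taken off study for a DLT are followed or censored for PFS6.

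In section 10.2, report PFS6 with and without progression based on the clinical row alone. Sections 9.1 and 12.1 must be reconciled on what happens when a decline is due to toxicity; which clinical rule applies is for the investigators.

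The cost is a footnote, one extra summary line and one new data item. Section 11.1 records attribution to study procedures and section 6.1 relation to study medication, but neither records attribution to tumor. The downside is that some unconfirmed clinical progressions will rest on the investigator's judgement.
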